4.3. Lifestyle Guidelines

In this study, male patients who are able to father children and female patients who are of childbearing potential will receive PF-06671008, a compound for which the teratogenic risk is currently unknown. Two (2) methods of highly effective contraception must be used throughout the study and continued for at least 28 days after the last dose of study treatment. The investigator or his or her designee, in consultation with the patient, will confirm the patient has selected two appropriate methods of contraception for the individual patient and his/her partner from the list of permitted contraception methods (see below) and will confirm the patient has been instructed in their consistent and correct use. Patients need to affirm that they meet the criteria for correct use of at least 2 of the selected methods of contraception. The investigator or his or her designee will discuss with the patient the need to use highly effective contraception consistently and correctly according to the [Schedule of Activities](#) and document such conversation in the patient's chart. In addition, the investigator or his or her designee will instruct the patient to call immediately if a selected contraception method is discontinued or if pregnancy is known or suspected in the patient or the patient's partner.

Highly effective methods of contraception are those that, alone or in combination, result in a failure rate of less than 1% per year when used consistently and correctly (ie, perfect use) and include the following:

1. Established use of oral, inserted, injected, implanted or transdermal hormonal methods of contraception is allowed provided the patient plans to remain on the same treatment throughout the entire study and has been using that hormonal contraceptive for an adequate period of time to ensure effectiveness.
2. Correctly placed copper-containing intrauterine device (IUD).
3. Male condom or female condom used WITH a spermicide (ie, foam, gel, film, cream, or suppository). For countries where spermicide is not available or condom plus spermicide is not accepted as highly effective contraception, this option is not appropriate.
4. Male sterilization with absence of sperm in the post vasectomy ejaculate.
5. Bilateral tubal ligation or bilateral salpingectomy or bilateral tubal occlusive procedure (provided that occlusion has been confirmed in accordance with the device's label).
6. Female partner who meets the criteria for non-childbearing potential, defined as:
 - Have undergone a documented hysterectomy and/or bilateral oophorectomy;
 - Have medically confirmed ovarian failure; or
 - Achieved postmenopausal status, defined as follows: cessation of regular menses for at least 12 consecutive months with no alternative pathological or physiological cause; status may be confirmed by having a serum follicle-stimulating hormone (FSH) level within the laboratory's reference range for postmenopausal women.

All sexually active male patients must agree to prevent potential transfer of and exposure to drug through semen to their partners by using a condom consistently and correctly, beginning with the first dose of investigational product and continuing for at least 28 days after the last dose.

4.4. Sponsor's Qualified Medical Personnel

The contact information for the sponsor's appropriately qualified medical personnel for the study is documented in the study contact list located in the study manual.

To facilitate access to appropriately qualified medical personnel on study-related medical questions or problems, patients are provided with a contact card. The contact card contains, at a minimum, protocol and investigational compound identifiers, patient study numbers, contact information for the investigational site, and contact details for a contact center in the event that the investigational site staff cannot be reached to provide advice on a medical question or problem originating from another healthcare professional not involved in the patient's participation in the study. The contact number can also be used by investigational staff if they are seeking advice on medical questions or problems; however, it should be used only in the event that the established communication pathways between the investigational site and the study team are not available. It is therefore intended to augment, but not replace,

the established communication pathways between the investigational site and the study team for advice on medical questions or problems that may arise during the study. The contact number is not intended for use by the patient directly, and if a patient calls that number, he or she will be directed back to the investigational site.

5. STUDY TREATMENTS

For the purposes of this study, and per International Conference of Harmonisation (ICH) guidelines investigational product is defined as a pharmaceutical form of an active ingredient or placebo being tested or used as a reference in a clinical trial, including a product with a marketing authorization when used or assembled (formulated or packaged) in a way different from the approved form, or when used for an unapproved indication, or when used to gain further information about an approved use (ICH E6 1.33).

5.1. Allocation to Treatment

Patient enrollment number and dose level allocation will be performed by the sponsor after patients have given their written informed consent and have completed the necessary baseline assessments. The site staff will email a complete Registration Form to the designated sponsor study team member. The sponsor will assign a patient identification number documenting patient enrollment. IV and SC routes of administration will be enrolled in parallel. Patients will be allocated to a dose escalation cohort and route of administration based on the sequential available slots.

No patient shall receive investigational product until the investigator or designee has received the following information in writing from the sponsor:

- confirmation of the patient's enrollment;
- specification of the dose level and route of administration for that patient and;
- permission to proceed with dosing the patient.

The sponsor or designee will notify the other sites of the inclusion of a new patient, and will inform study sites about the next possible enrollment date.

5.2. Patient Compliance

All doses of investigational product will be administered by the appropriately designated study staff at the investigational site.

The site will complete required dosage Preparation Record located in the study manual. The use of the Preparation Record is preferred but it does not preclude the use of an existing appropriate clinical site documentation system. The existing clinical site's documentation system should capture all pertinent/required information on the preparation and administration of the dose. This may be used in place of the Preparation Record after approval from the Pfizer monitor.

5.3. Investigational Product Supplies

5.3.1. Dosage Form(s) and Packaging

PF-06671008 solution for injection, 1 mg/mL is presented as a sterile solution for IV or SC administration. Each vial contains 1 mg of PF-06671008 in 1 mL of aqueous buffered solution, is sealed with a coated stopper and an overseal, and is labeled according to local regulatory requirements.

[figure not shown]
[figure not shown]
5.3.2. Preparation and Dispensing

See the Investigational Product (IP) Manual for instructions on how to prepare the investigational product for administration and how to handle the investigational product once it is prepared for administration. Investigational product should be prepared and dispensed by an appropriately qualified and experienced member of the study staff (eg, physician, nurse, physician's assistant, practitioner, pharmacist, or medical assistant) as allowed by local, state, and institutional guidance.

Vials are for single-use, single-patient only.

5.4. Administration

CCI

CCI

[REDACTED]

[REDACTED]

[REDACTED]

[REDACTED]

[REDACTED]

5.4.1. Cytokine Release Syndrome

Symptoms associated with CRS vary greatly and may be difficult to distinguish from other conditions. The more common symptoms include fever, nausea, headache, tachycardia, hypotension, rash and shortness of breath. The severity of symptoms can be mild to life threatening and thus, there should be a high suspicion for CRS if these symptoms occur. Grade 1 CRS does not require any intervention but patients should be monitored closely. Grade ≥ 2 CRS requires PF-06671008 infusion interruption and prompt symptomatic treatment per local standard of care. For CRS not rapidly responsive to supportive care or CRS of Grade ≥ 3 , treatment with corticosteroids and/or tocilizumab,² an anti-human IL-6R mAb, should be considered.¹² A suggested treatment algorithm for the management and grading of CRS based on a revised CRS grading system by Lee et al. is provided in [Appendix 8](#).

The decision to incorporate pre-medication (ie, corticosteroids) for CRS prophylaxis in all patients will be made following discussions between the sponsor and the investigators. The pre-treatment medication will not be supplied by Pfizer.

5.4.2. Infusion Reactions

In the case of infusion related reactions, characterized by fever and chills, and less commonly hypotension, the sponsor should be notified and adjustment of infusion rate may be considered, which could include interrupting the infusion or slowing the infusion rate to a previously acceptable rate by increasing duration of the infusion. When the infusion rate is adjusted to a previously acceptable rate for 2 or more patients at the current cohort, the sponsor should be notified and the infusion rates for current and subsequent cohorts should be maintained at the previously acceptable rate.

In addition, pre-treatment medication should be administered prior to subsequent infusions (in the case that the patient is able to continue on treatment). The decision to incorporate pre-medication for infusion related reaction prophylaxis in all patients will be made following discussions between the sponsor and the investigators. Patients should be pre-treated with acetaminophen and diphenhydramine (or other antihistamine) approximately 0.5 to 2 hours before each PF-06671008 administration. The pre-treatment medication will not be supplied by Pfizer.

Suggested starting doses are 650 to 1000 mg acetaminophen and 50 mg diphenhydramine (or equivalent of other antihistamine) IV or oral. Two additional doses of acetaminophen may be administered approximately every 4 hours after the initial pre-treatment or as needed.

5.4.3. Hypersensitivity Types 1 and 3

Type 1 hypersensitivity or allergic (eg, shortness of breath, urticaria, anaphylaxis, angioedema) reactions are theoretically possible in response to any injected protein. Immune complex mediated Type 3 hypersensitivity reactions are similar to the adverse events (AEs) of Type 1 reactions but are likely to be delayed from the time of infusion and may include symptoms such as rash, urticaria, polyarthritis, myalgias, polysynovitis, fever, and, if severe, glomerulonephritis.

All patients should be closely observed while receiving investigational product and monitoring for clinical signs of a systemic reaction will continue thereafter for clinical signs of allergic reactions/hypersensitivity.

In the case of a hypersensitivity reaction, the patient will be treated symptomatically with supportive care, further monitoring, and treatment with anti-histamines and/or corticosteroids. Study administration may be stopped and the patient will be followed until the end of the study.

5.4.4. Extravasation

In the event of extravasation, infusion should be stopped immediately and the investigator needs to be consulted immediately. Treatment of extravasation should follow local standard of care.

5.4.5. Recommended Dose Modifications

Every effort should be made to administer investigational product on the planned dose and schedule.

In the event of significant toxicity dosing may be delayed and/or reduced as described below. In the event of multiple toxicities, dose modification should be based on the worst toxicity observed. Patients are to be instructed to notify investigators at the first occurrence of any adverse symptom.

Dose modifications may occur in one of three ways:

- Within a cycle: dosing interruption until adequate recovery and dose reduction, if required, during a given treatment cycle;
- Between cycles: next cycle administration may be delayed due to persisting toxicity when a new cycle is due to start;
- In the next cycle: dose reduction may be required in a subsequent cycle based on toxicity experienced in the previous cycle.

5.4.6. Dosing Interruptions

Patients experiencing Grade 3 or 4 potentially treatment related toxicity or intolerable Grade 2 toxicity despite supportive care should have their treatment interrupted.

Appropriate follow up assessments should be done until adequate recovery occurs as assessed by the investigator. Criteria required before treatment can resume are described in the [Dose Delays](#) section.

Doses may be held as needed until toxicity resolution. Depending on when the AE resolved, a treatment interruption may lead to the patient missing all subsequent planned doses within that same cycle or even to delay the initiation of the subsequent cycle.

If the adverse event that led to the treatment interruption recovers within the same cycle, then re-dosing in that cycle is allowed. Doses omitted for toxicity are not replaced within the same cycle. The need for a dose reduction at the time of treatment resumption should be based on the criteria defined in the [Dose Reductions](#) section, unless expressly agreed otherwise following discussion between the investigator and the sponsor.

In the event of a treatment interruption for reasons other than treatment-related toxicity (eg, elective surgery) lasting >2 weeks, treatment resumption will be decided in consultation with the sponsor.

5.4.7. Dose Delays

Re-treatment following treatment interruption for treatment-related toxicity or at the start of any new cycle may not occur until all of the following parameters have been met:

- ANC $\geq 1,000/\text{mm}^3$.
- Platelets count $\geq 50,000/\text{mm}^3$.
- Non-hematologic toxicities have returned to baseline or Grade ≤ 1 severity (or, at the investigator discretion, Grade ≤ 2 if not considered a safety risk for the patient).

If a treatment delay results from worsening of hematologic or biochemical parameters, the frequency of relevant blood tests should be increased as clinically indicated.

If these conditions are met within 14 days of treatment interruption or cycle delay, PF-06671008 may be resumed. Refer to Section Dose Reductions for AEs requiring dose reduction at the time of treatment resumption.

If treatment interruption due to toxicity exceeds 14 days, treatment with this agent should be permanently discontinued.

The day when the patient receives their 4th dose of study drug will be counted as Day 1 of the next cycle. Subsequent cycles will be 21 days in length regardless of treatment delays.

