5.4.8. Dose Reductions

Following dosing interruption or cycle delay due to toxicity, the PF-06671008 dose may need to be reduced when treatment is resumed.

No specific dose adjustments are recommended for Grade 1 treatment-related toxicity. However, investigators should always manage their patients according to their medical judgment based on the particular clinical circumstances.

Dose reduction of PF-06671008 by 1 and, if needed, 2 dose levels will be allowed depending on the type and severity of toxicity encountered. Patients enrolled in the first cohort should be discontinued from the study if more than 1 dose reduction is required. Patients requiring more than 2 (or 1 for the first cohort) dose reductions will be discontinued from the treatment and entered into the follow-up phase, unless otherwise agreed between the investigator and the sponsor. All dose modifications/adjustments must be clearly documented in the patient's source notes and CRF.

Once a dose has been reduced for a given patient, all subsequent cycles should be administered at that dose level, unless further dose reduction is required. Dose re-escalation is not allowed.

Patients experiencing a DLT may resume dosing at the next lower dose level (if applicable) once adequate recovery is achieved.

Recommended dose reductions are described in Table 3.

Table 3. Dose Reductions

Event	Action
Grade 3 or 4 non-hematologic toxicity (except CRS) considered related to PF-06671008 per investigator judgment (including persistent nausea, vomiting, diarrhea despite optimal medical therapy), excluding clinically manageable electrolyte abnormalities.	
 Hold PF-06671008 until recovery to Grade 0-1 or baseline and reduce by 1 dose level. If toxicity (Grade 3-4) reoccurs despite reduction, patient may be dose reduced again by 1 more dose level (except for the first cohort) upon recovery to Grade 0-1 or baseline. Prompt palliative and supportive measures mandated per local standard of care (eg, antiemetic). Patients who experience Grade 4 non hematologic toxicities despite intervention should be discontinued from study treatment, unless restarting treatment at reduced dose level is in the patient's best interest per investigator judgment and after consultation with Pfizer's medical monitor (eg, clear clinical benefit and no alternative treatment options).

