Cytokine Release Syndrome	
 Grade 2: Hold PF-06671008 until resolved and resume at same dose level. If Grade 2 CRS reoccurs, hold PF-06671008 until resolved and consider reduction by 1 dose level based on the investigator's discretion. Grade 3: Hold PF-06671008 until resolved and consider reduction by 1 dose level based on the investigator's discretion. If Grade 3 CRS recurs despite reduction, permanently discontinue PF-06671008. Grade 4: Permanently discontinue PF-06671008.
Hematologic toxicity considered related to PF-06671008 per investigator judgment 
 Grade 4 neutropenia, ie, ANC <500 mm³ (1.0 x 10⁹/L) for more than 5 days or Febrile neutropenia, ie, fever >38.3°C (101°F) or a sustained temperature of ≥38°C (100.4°F) with ANC <1000/mm³ or Grade ≥3 neutropenic infection or Grade 4 Thrombocytopenia, ie, PLTS <25,000 mm³ (25.0 x 10⁹/L) or Grade 3 Thrombocytopenia, ie, PLTS <50,000 mm³ (50.0 x 10⁹/L) with bleeding. 	
 Hold PF-06671008 until recovery of ANC to ≥1.0 x 10⁹/L (1,000 cells/mm³) and platelets ≥75 x 10⁹/L (75,000 cells/mm³). Reduce PF-06671008 by 1 dose level. If toxicity reoccurs (grades as described on the left side) despite dose reduction, patients may either be held until recovery and continuation at same dose, or undergo further dose reduction by 1 more dose level (except for the first cohort).
Other grade 4 hematologic toxicity considered related to PF-06671008 per investigator judgment	
 Hold PF-06671008 until recovery to Grade 0-1 or baseline and reduce PF-06671008 dose by 1 dose level. If toxicity reoccurs (Grade 4) despite dose reduction, patient may either be held until recovery and continuation at same dose, or undergo further dose reduction by 1 more dose level.
No recovery of toxicities within 4 weeks of scheduled PF-06671008 infusion	
 Discontinue treatment, unless restarting treatment at reduced dose level is in the patient's best interest per investigator judgment and after consultation with Pfizer's medical monitor (eg, clear clinical benefit and no alternative treatment options).

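### For the events listed in Protocol Table 3, Sections 5.4.7 and 5.4.8 give different recovery criteria for resuming treatment, and nothing says which prevails

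*Protocol*

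**What the plan says.** Protocol 5.4.6 (Dosing Interruptions) requires treatment to be interrupted for potentially related Grade 3 or 4 toxicity and for intolerable Grade 2 toxicity. It then sends the reader elsewhere for the restart rule: "Criteria required before treatment can resume are described in the [Dose Delays](#) section".

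Protocol 5.4.7 (Dose Delays) applies to every restart after an interruption for treatment-related toxicity and to the start of any new cycle. Re-treatment "may not occur until all of the following parameters have been met": ANC of at least 1,000/mm³, platelets of at least 50,000/mm³, and non-haematologic toxicity at baseline or Grade 1 or lower. Grade 2 is acceptable at the investigator's discretion "if not considered a safety risk for the patient". The section also treats these conditions as enough: "If these conditions are met within 14 days of treatment interruption or cycle delay, PF-06671008 may be resumed". An interruption for toxicity of more than 14 days means permanent discontinuation.

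Protocol 5.4.8 (Dose Reductions), Table 3, gives event-specific actions:
- For related Grade 3 or 4 non-haematologic toxicity other than CRS: "Hold PF-06671008 until recovery to Grade 0-1 or baseline and reduce by 1 dose level".
- For the listed related haematologic toxicities (prolonged Grade 4 neutropenia, febrile neutropenia, Grade 3 or higher neutropenic infection, Grade 4 thrombocytopenia, Grade 3 thrombocytopenia with bleeding): hold until ANC is at least 1,000/mm³ and "platelets ≥75 x 10⁹/L (75,000 cells/mm³".
- For toxicity not recovered within 4 weeks of the scheduled infusion: discontinue, with an exception after consultation with the medical monitor.

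**The concern.** Each list is a restart rule, and for the Table 3 events both apply to the same decision. A site that follows 5.4.6 to 5.4.7 finds conditions that permit resumption. A site that looks up the event in Table 3 finds an instruction to keep holding. The same patient could therefore be re-dosed at one site and held at another, in a first-in-patient study planned for about six sites (Protocol 9.3).

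What is at stake is mainly consistency in a re-dosing safety decision. The rule a site follows also feeds the delay, interruption and reduction summaries in SAP 6.1. It can affect discontinuations too, because a longer hold may pass the 14-day limit in 5.4.7. A smaller question is whether it changes DLT counts, since Protocol 3.3 makes a delay of more than 2 weeks for persisting related toxicity a DLT.

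**Working it through.** No figure in the plan needs to be reproduced. The check sets the passages side by side, with one unit conversion.

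**1. Criteria compared, for events that Table 3 lists**

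| Item | 5.4.7 | Table 3 |
|---|---|---|
| ANC | ≥1,000/mm³ | ≥1,000/mm³ |
| Platelets | ≥50,000/mm³ | ≥75,000/mm³ (listed haematologic events) |
| Non-haematologic, default | baseline or Grade ≤1 | Grade 0-1 or baseline (related Grade 3-4, not CRS) |
| Non-haematologic, exception | Grade 2 at investigator discretion if not a safety risk | none in this row |
| Time limit | discontinue after 14 days | discontinue if no recovery within 4 weeks, exception possible |

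Conversion: 1 × 10⁹/L = 1,000/mm³, so 75 × 10⁹/L = 75,000/mm³. The gap is 75,000 − 50,000 = 25,000/mm³, and the ratio is 75,000 / 50,000 = 1.5. The ANC threshold and the default non-haematologic rule agree. The differences are the platelet threshold, the Grade 2 exception and the time limit.

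**2. Patients for whom the answer differs**
- After a listed haematologic event such as Grade 4 thrombocytopenia, with platelets at 60,000/mm³ and the other 5.4.7 conditions met: 5.4.7 permits resumption, and Table 3 says hold.
- After a related Grade 3 non-haematologic event that has settled to Grade 2, with baseline Grade 0-1: 5.4.7 permits resumption at the investigator's discretion, and Table 3 says hold. If baseline was already Grade 2, the two agree.

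**3. Does any cross-reference settle it?** Section 5.4.6 names 5.4.7 for resumption criteria and 5.4.8 for the need to reduce. Section 5.4.7 makes the same split: "Refer to Section Dose Reductions for AEs requiring dose reduction at the time of treatment resumption". Neither sends the reader to Table 3 for a different recovery threshold, and no passage states an order of precedence.

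**4. Reach into DLTs.** The Table 3 haematologic triggers were compared with the DLT list in Protocol 3.3, for events in Cycle 1:
- Grade 4 neutropenia for more than 5 days: already a DLT (3.3 uses 5 days or more).
- Febrile neutropenia, Grade 3 or higher neutropenia with infection, and Grade 4 thrombocytopenia: already DLTs.
- Grade 3 thrombocytopenia with bleeding: already a DLT if the bleeding is Grade 2 or higher. Grade 1 bleeding is the clear exception.

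Among non-haematologic events, clinically significant Grade 4 toxicity, and clinically significant Grade 3 toxicity lasting more than 72 hours despite maximal supportive care, are already DLTs. One case left over is a Grade 3 event that improves to Grade 2 within 72 hours and then stays at Grade 2 for more than 2 weeks. In these remaining cases the criterion applied can decide whether a delay-based DLT is recorded, provided the delay is attributed to Cycle 1. With 3 patients at a dose, going from 0 to 1 DLT changes the Protocol Table 2 decision from escalate to stay.

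**5. Time limits.** 4 weeks is 28 days, and 28 − 14 = 14 days. A patient who meets the recovery criteria on day 20 of a toxicity-related interruption must stop permanently under 5.4.7. If that day also falls within 4 weeks of the scheduled infusion, the Table 3 row has not been triggered. The two limits also start from different points: the interruption or cycle delay in 5.4.7, and the scheduled infusion in Table 3.

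**The case against.** The strongest defence is that the passages can be obeyed together. Section 5.4.7 would be a general minimum, and Table 3 would add a condition after more severe events. Anyone who meets the Table 3 platelet or grade condition also meets the corresponding item in 5.4.7. That reading is possible, but the text does not state it. Section 5.4.7 says that meeting its own conditions allows resumption, 5.4.6 names it as the source of the criteria, and Table 3 is introduced as recommended dose reductions. Nor does the reading explain the time limits, where the general section is the more restrictive one.

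Three points on scope do stand:
- A reader might infer that both lists cover every interruption. They do not. Table 3 covers only its listed related events. A patient with platelets of 60,000/mm³ and no such event falls under 5.4.7 alone.
- A reader might infer that the non-haematologic rules differ by a full CTCAE grade as standard. The default is the same in both places. Only the conditional Grade 2 exception in 5.4.7 differs.
- A reader might infer a general effect on delay-based DLTs. Most of the triggering events are already DLTs under 3.3, so the documents support only a narrow effect.

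**Conclusion.** The inconsistency is real for the events listed in Table 3, and it is one of wording between sections, not a design choice. The size is 25,000/mm³ on platelets, plus a Grade 2 exception that exists in one passage and not in the other. It mainly affects re-dosing safety and the recorded delays and interruptions. The effect on DLTs is confined to the few events not already covered by 3.3.

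The conclusion assumes that the current text of 5.4.6 to 5.4.8 is all that governs resumption. The study manual and the Investigational Product Manual are not among the documents. The number of patients affected cannot be estimated from the documents. Nothing here bears on which threshold is clinically right.

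**What to change.** The passages must be reconciled. Either state one set of resumption criteria, or state in 5.4.7 and Table 3 which events each set covers and which prevails where both apply. The cross-references in 5.4.6 and 5.4.7 should then point to the governing text. In the same amendment, reconcile the 14-day discontinuation rule in 5.4.7 with the 4-week row in Table 3, including the day from which each is counted. The choice of criteria and limits belongs to the sponsor's clinical team.

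The cost is wording in a protocol amendment. Sample size and analysis methods do not change.
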